**B: Tables for Laboratory Abnormalities**

The grading scale used for laboratory assessments is based on the FDA Guidance document “Toxicity Grading Scale from Healthy Adult and Adolescent Volunteers Enrolled in Preventive Vaccine Clinical Trials”. Any laboratory value shown as a “graded” value in the table that is within the central laboratory normal ranges will not be graded for severity or recorded as AE. For hemoglobin, both the actual value and the change from reference will be graded. For the change from reference, the corresponding actual value should also be at least Grade 1.

Serum *	Mild (Grade 1)	Moderate (Grade 2)	Severe (Grade 3)	Potentially Life-threatening (Grade 4) **
Sodium – Hyponatremia - mEq/L	132 – 134	130 – 131	125 – 129	< 125
Sodium – Hypernatremia - mEq/L	144 – 145	146 – 147	148 – 150	> 150
Potassium – Hyperkalemia - mEq/L	5.1 – 5.2	5.3 – 5.4	5.5 – 5.6	> 5.6
Potassium – Hypokalemia - mEq/L	3.5 – 3.6	3.3 – 3.4	3.1 – 3.2	< 3.1
Glucose – Hypoglycemia - mg/dL	65 – 69	55 – 64	45 – 54	< 45
Glucose – Hyperglycemia Fasting - mg/dL	100 – 110	111 – 125	> 125	Insulin requirements or hyperosmolar coma
Random Glucose - mg/dL	110 – 125	126 – 200	>200	
Blood Urea Nitrogen BUN - mg/dL	23 – 26	27 – 31	> 31	Requires dialysis
Creatinine - mg/dL	1.5 – 1.7	1.8 – 2.0	2.1 – 2.5	> 2.5 or requires dialysis
Calcium – hypocalcemia - mg/dL	8.0 – 8.4	7.5 – 7.9	7.0 – 7.4	< 7.0
Calcium – hypercalcemia - mg/dL	10.5 – 11.0	11.1 – 11.5	11.6 – 12.0	> 12.0
Magnesium – hypomagnesemia - mg/dL	1.3 – 1.5	1.1 – 1.2	0.9 – 1.0	< 0.9
Phosphorous – hypophosphatemia - mg/dL	2.3 – 2.5	2.0 – 2.2	1.6 – 1.9	< 1.6
CPK - mg/dL	1.25 – 1.5 x ULN***	1.6 – 3.0 x ULN	3.1 –10 x ULN	> 10 x ULN
Albumin – Hypoalbuminemia - g/dL	2.8 – 3.1	2.5 – 2.7	< 2.5	--

Serum *	Mild (Grade 1)	Moderate (Grade 2)	Severe (Grade 3)	Potentially Life- threatening (Grade 4) **
Total Protein – Hypoproteinemia - g/dL	5.5 – 6.0	5.0 – 5.4	< 5.0	--
Alkaline phosphate – increase by factor	1.1 – 2.0 x ULN	2.1 – 3.0 x ULN	3.1 – 10 x ULN	> 10 x ULN
Liver Function Tests – ALT, AST increase by factor	1.1 – 2.5 x ULN	2.6 – 5.0 x ULN	5.1 – 10 x ULN	> 10 x ULN
Bilirubin – when accompanied by any increase in Liver Function Test increase by factor	1.1 – 1.25 x ULN	1.26 – 1.5 x ULN	1.51 – 1.75 x ULN	> 1.75 x ULN
Bilirubin – when Liver Function Test is normal; increase by factor	1.1 – 1.5 x ULN	1.6 – 2.0 x ULN	2.0 – 3.0 x ULN	> 3.0 x ULN
Cholesterol	201 – 210	211 – 225	> 226	--

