### **5.2. Clinical Laboratory Tests**

For laboratory safety parameters, only abnormalities emerging after vaccination will be tabulated by worst abnormality grade using the FDA table in [Attachment 1](#).

An abnormality (toxicity grade or abnormality based on normal ranges) will be considered as emerging in a particular period if it is worse than the baseline value. If the baseline is missing, the abnormality is always considered emerging. A shift from ‘abnormally low’ at baseline to ‘abnormally high’ post baseline (or vice versa) is also emerging. In case a laboratory test result is censored (no numeric value is available, but only a verbatim term) then a numeric value will be imputed by a value exceeding the cut-off value with one unit. (<x: subtract 1 unit from x, >x: add 1 unit to x; <3.45 is imputed with 3.44).

In case no toxicity grades are defined for a test, the abnormalities (above/below normal range) will be used. In determining toxicity grades, the following rules are applied:

- worst grades/abnormalities are determined over the whole observational period for each trial period separately, including all post-baseline measurements of that period.
- The abnormalities ‘abnormally low’ and ‘abnormally high’ are considered equally important, i.e. if a subject has as well an abnormally low as an abnormally high value post-baseline, both abnormalities are shown in the tables. (This means that the sum of the percentages can be more than 100%)
- Note: as the grading scale for some parameters in the grading table has some gaps (zones where no toxicity grade definition exists), laboratory results falling in these zones will be allocated to the adjacent worst-case grade.
- If a lab value falls within the grading as specified in the grading table but also within the local lab normal limits, the value is considered as normal.

For the grades, no distinction will be made between test results of samples obtained under fasting and under non-fasting conditions: in case limits under fasting and non-fasting conditions differ, the limits of the conditions (fasting/non-fasting) of scheduled visits as planned in the CTP will always be used, also for samples obtained under a different condition (e.g. samples of withdrawal visits).

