Serum *	Mild (Grade 1)	Moderate (Grade 2)	Severe (Grade 3)	Potentially Life Threatening (Grade 4)**
Alkaline phosphate – increase by factor	1.1 – 2.0 x ULN	2.1 – 3.0 x ULN	3.1 – 10 x ULN	> 10 x ULN
Liver Function Tests –ALT, AST increase by factor	1.1 – 2.5 x ULN	2.6 – 5.0 x ULN	5.1 – 10 x ULN	> 10 x ULN
Bilirubin – when accompanied by any increase in Liver Function Test increase by factor	1.1 – 1.25 x ULN	1.26 – 1.5 x ULN	1.51 – 1.75 x ULN	> 1.75 x ULN
Bilirubin – when Liver Function Test is normal; increase by factor	1.1 – 1.5 x ULN	1.6 – 2.0 x ULN	2.0 – 3.0 x ULN	> 3.0 x ULN
Cholesterol	201 – 210	211 – 225	> 226	---
Pancreatic enzymes – amylase, lipase	1.1 – 1.5 x ULN	1.6 – 2.0 x ULN	2.1 – 5.0 x ULN	> 5.0 x ULN

\* The laboratory values provided in the tables serve as guidelines and are dependent upon institutional normal parameters. Institutional normal reference ranges should be provided to demonstrate that they are appropriate.

\*\* The clinical signs or symptoms associated with laboratory abnormalities might result in characterization of the laboratory abnormalities as Potentially Life Threatening (Grade 4). For example, a low sodium value that falls within a grade 3 parameter (125-129 mE/L) should be recorded as a grade 4 hyponatremia event if the subject had a new seizure associated with the low sodium value.

\*\*\*"ULN" is the upper limit of the normal range.

Hematology *	Mild (Grade 1)	Moderate (Grade 2)	Severe (Grade 3)	Potentially Life Threatening (Grade 4)
Hemoglobin (Female) - gm/dL	11.0 – 12.0	9.5 – 10.9	8.0 – 9.4	< 8.0
Hemoglobin (Female) change from baseline value - gm/dL	Any decrease – 1.5	1.6 – 2.0	2.1 – 5.0	> 5.0
Hemoglobin (Male) - gm/dL	12.5 – 13.5	10.5 – 12.4	8.5 – 10.4	< 8.5
Hemoglobin (Male) change from baseline value – gm/dL	Any decrease – 1.5	1.6 – 2.0	2.1 – 5.0	> 5.0
WBC Increase - cell/mm 	10,800 – 15,000	15,001 – 20,000	20,001 – 25,000	> 25,000
WBC Decrease - cell/mm 	2,500 – 3,500	1,500 – 2,499	1,000 – 1,499	< 1,000
Lymphocytes Decrease - cell/mm 	750 – 1,000	500 – 749	250 – 499	< 250
Neutrophils Decrease - cell/mm 	1,500 – 2,000	1,000 – 1,499	500 – 999	< 500
Eosinophils - cell/mm 	650 – 1500	1501 - 5000	> 5000	Hypereosinophilic
Platelets Decreased - cell/mm 	125,000 – 140,000	100,000 – 124,000	25,000 – 99,000	< 25,000

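### The SAP grades any fall in adult haemoglobin without the protocol's condition on the actual value, and does not say whether its normal-limits rule covers the change rows

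*SAP*

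**What the plan says.** Protocol Attachment 1, part B, grades both the actual haemoglobin value and its change from reference, and limits the second: "For the change from reference, the corresponding actual value should also be at least Grade 1". The same paragraph separately says that a value "within the central laboratory normal ranges will not be graded for severity or recorded as AE".

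The haematology table in SAP Attachment 1 keeps both kinds of row. The actual-value row ("Hemoglobin (Female) - gm/dL", with a matching male row) sets Grade 1 at 11.0 to 12.0 g/dL for women and 12.5 to 13.5 g/dL for men. The change rows ("Hemoglobin (Female) change from baseline value - gm/dL" and the male equivalent) set Grade 1 as "Any decrease – 1.5", Grade 2 as 1.6 to 2.0 and Grade 3 as 2.1 to 5.0 g/dL. No condition on the actual value appears in the attachment or in SAP 5.2.

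SAP 5.2 states that "only abnormalities emerging after vaccination will be tabulated by worst abnormality grade using the FDA table", and treats anything worse than baseline as emerging. It adds that a value the table would grade, "but also within the local lab normal limits, the value is considered as normal". The header of SAP Attachment 1 repeats this rule. SAP 1.6, which lists changes to the planned analyses, does not mention haemoglobin.

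**The concern.** The two documents state different grading rules for one laboratory parameter, and the difference is not declared. SAP section 1 presents the SAP as complete for the safety analysis, so a programmer has no reason to go back to the protocol for a missing condition.

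Read alone, the SAP's change rows turn any measurable fall into at least a Grade 1 post-vaccination abnormality. Some fall is likely even without a vaccine effect. Haemoglobin varies from day to day, and the only scheduled post-baseline haematology sample (Day 8) follows a large research blood draw on Day 1. Cohort 0 is the only cohort with safety laboratory data and is the check on the new formulation buffer. Protocol 3.4.4 names decreased haemoglobin among the transient changes seen with Ad26-vectored vaccines. The tabulation of this parameter should therefore follow the rule the protocol set.

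**Working it through.** **Inputs from the documents.** Cohort 0 has 12 adults, 8 active and 4 placebo. Haematology is taken at screening, before dosing on Day 1 and on Day 8 (Protocol 9.2.3.2). Baseline is the last assessment before first vaccination (SAP 2.1), which is the Day 1 pre-dose sample. The blood volumes in the Cohort 0 schedule add up: screening 10 + 15 = 25 mL; Day 1 5 + 40 + 40 = 85 mL; cumulative 110 mL on Day 1 and 115 mL on Day 8. The 25 mL at screening precedes baseline and cannot cause a fall from it, so 85 mL is the relevant draw.

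**Assumptions, because the documents give no haemoglobin distribution or local limits.** For the simple formula: haemoglobin 14.5 g/dL, blood volume 5 L, SD of the difference 0.3 to 0.7 g/dL. For the simulation (400,000 draws per sex, sexes weighted equally): mean 15.0 (SD 1.0) in men and 13.4 (SD 0.9) in women; within-subject SD 0.3 to 0.6 g/dL per measurement; shift 0 to 0.25 g/dL; values rounded to 0.1; baseline no worse than Grade 1; three sets of local lower limits.

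**Reading A: change rows stand alone, outside the normal-limits rule.**
- Expected fall from the draw: 14.5 × 85 / 5000 = 0.25 g/dL.
- Probability of a recorded fall of at least 0.1 g/dL: Φ((0.25 − 0.05)/SD). SD 0.7 gives Φ(0.29) = 61%; SD 0.3 gives Φ(0.67) = 75%. Times 12, that is about 7 to 9 adults.
- The simulation, which also allows no shift at all, gives 45% to 68%, or 5.4 to 8.2 of 12. Grade 2 or higher occurs in 0 to 6%.
- Together: about 5 to 9 of 12.
- At a probability of 50%, 4 of 8 active and 2 of 4 placebo subjects are expected. At least one is flagged with probability 1 − 0.5⁸ = 99.6% and 1 − 0.5⁴ = 93.8%. These match the 50% row of the table in Protocol 11.2 (100% and 94%).

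**Reading B: SAP with the normal-limits rule applied to the actual value. Reading C: protocol condition plus normal-range rule.** Expected adults of 12 with a graded fall:

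| Local lower limit, men/women (g/dL) | B: SAP | C: protocol | Difference |
|---|---|---|---|
| 13.0 / 11.5 | 0.2–0.6 | 0.2–0.6 | 0 |
| 13.5 / 12.0 | 0.5–1.3 | 0.5–1.3 | 0 |
| 14.0 / 12.3 | 0.9–2.1 | 0.6–1.5 | 0.4–0.7 |

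B and C agree when the local limit is at or below the top of FDA Grade 1, because an out-of-range value is then already Grade 1. They part only above it. For example, with an assumed male limit of 14.0, a man who falls from 15.9 to 13.8 g/dL is out of range but above the 12.5 to 13.5 band. The protocol gives no change grade; the SAP gives Grade 3 for the fall of 2.1.

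**The case against.** The strongest reply is that the SAP already deals with most of this. Its normal-limits rule appears in SAP 5.2 and again at the head of the attachment that holds the change rows. What the laboratory reports is a haemoglobin concentration, so an in-range Day 8 value can naturally be called normal whichever row would have graded it. Protocol 9.2.3.2 also leaves values within local limits ungraded. On that reading the gap is at most about 0.7 of 12 adults, and nil for many plausible local limits.

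This is a fair reading and it removes most of the effect, but it does not settle the point. A change from baseline has no normal limits, and the SAP does not say that the rule governs the change rows. The protocol puts the normal-range rule and the haemoglobin condition in the same paragraph, so it does not treat the first as making the second unnecessary.

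A reader might go further and infer that most adults will be tabulated with a haemoglobin abnormality and that a real signal would be hidden. The documents do not support that. It assumes Reading A, whose lower end is under half of the adults. The extra entries are nearly all Grade 1, and a table by worst grade keeps them apart from higher grades. Both arms are affected alike, and the SAP plans no formal comparison. No safety decision is tied to this table: recording a laboratory value as an AE requires clinical significance, and pausing rule 5 requires persistent Grade 3 or 4 abnormalities, judged related, in at least two subjects.

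**Conclusion.** The SAP is wrong as written, with low impact. It keeps the change-from-baseline rows, omits the protocol's condition on the actual value, does not declare the change, and does not say whether its normal-limits rule covers those rows.

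If the rule does not cover them, about 5 to 9 of 12 adults could be tabulated with a haemoglobin abnormality at Day 8 through chance variation and the 85 mL draw. If it does, the SAP grades about 0 to 0.7 of 12 adults more than the protocol would, all with a value outside local limits but not FDA Grade 1. The omission of the condition is certain from the texts. The counts depend on the assumed haemoglobin distribution, SD, blood volume and local limits. The consequence is inflated low-grade counts in a descriptive table, not bias between arms.

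**What to change.** Add the protocol's condition to SAP 5.2 and to the haematology table in SAP Attachment 1: the change-from-baseline grade counts only if the actual haemoglobin value is at least Grade 1. State in the same place that, for these rows, the normal-limits rule is applied to the actual value. If the sponsor intends to depart from the protocol, say so in SAP 1.6 with the reason.

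The cost is a short addition to the SAP text and one programming condition. No new data are needed.

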**Attachment 2: Toxicity tables for cohort 1**

Grading scale used for clinical AEs is adapted from the Division of Microbiology and Infectious Diseases (DMID) “Pediatric Toxicity Tables for Children Greater Than 3 Months of Age (2007)”. For AEs not included in the tables below, severity criteria guidelines will be provided in the full protocol.

Gastrointestinal	Grade 1	Grade 2	Grade 3	Grade 4
Nausea/vomiting	Minimal symptoms; caused minimal or no interference with, school or self-care activities. Child vomits once per day (24h).	Notable symptoms; required modification in activity or use of medications; did not result in cancellation of social activities. Child vomits 2-3 times per day (24h).	Incapacitating symptoms; required bed rest and/or resulted in cancellation of social activities. Child vomits 4-6 times per day (24h).	Unable to ingest food or fluid for more than 24 hours/ $\geq 7$ episodes of vomiting per day or intractable vomiting. Emergency room visit or hospitalization and significant medical intervention/therapy required.
Diarrhea	Consistency of stools changes OR increase of 1-3 stools compared to normal frequency over a 24 hour period.	Liquid stools OR increase of 4-6 stools compared to normal frequency over a 24 hour period.	Increase of $\geq 7$ stools compared to normal frequency over a 24 hour period OR child might need an infusion with fluid without hospitalization.	Emergency room visit or hospitalization and significant medical intervention/therapy required.
Appetite	Some loss of appetite but no decrease in oral intake.	Loss of appetite associated with decreased oral intake.	Almost no appetite, does not eat and/or weight loss.	Emergency room visit or hospitalization and significant medical intervention/therapy required.

Reactogenicity	Grade 1	Grade 2	Grade 3	Grade 4
Systemic reactions				
Irritable/Fussy/Crying/ Screaming	Easily consoled and returns to play easily. He/she has periods of crying fewer than 60 minutes.	Not easily consoled and is not easily interested in playing. He/she has periods of crying lasting between 60-120 minutes.	Very irritable, cannot be consoled and does not play. He/she has periods of continuous crying lasting more than 2 hours.	Inconsolable. Emergency room visit or hospitalization and significant medical intervention/therapy required.
Lethargy	Minimal symptoms; caused minimal or no interference with school or activities.	Notable symptoms; required modification in activity or use of medications; did not result in loss school or cancellation of social activities.	Incapacitating symptoms; required bed rest and/or resulted in loss of school or cancellation of social activities.	Emergency room visit or hospitalization and significant medical intervention/therapy required.

Other	Grade 1	Grade 2	Grade 3	Grade 4
Fever	38.0-38.4 °C or 100.4-101.1 °F.	38.5-40 °C or 101.2-104.0 °F.	Greater than 40 °C or 104.0 °F.	Sustained Fever: equal or greater than 40C (104.0F) for longer than 5 days.

Reactogenicity	Grade 1	Grade 2	Grade 3	Grade 4
Local reactions				
Pain/tenderness at injection site	Mild discomfort when the injection site is touched; child does not limit use of his/her arm or leg where the injection was done.	Notable discomfort when the injection site is touched; child limits use of his/her arm or leg where the injection was done.	Severe discomfort when the injection site is touched; child avoids use of his/her arm or leg where the injection was done.	Emergency room visit or hospitalization and significant medical intervention/therapy required.
Erythema/redness	≥10 and <25 mm diameter.	≥25 and <50 mm diameter.	≥50mm diameter.	Emergency room visit or hospitalization; necrosis or exfoliative dermatitis.
Induration/swelling	≥10 and <25 mm diameter.	≥25 and <50 mm diameter.	≥50mm diameter.	Emergency room visit or hospitalization; necrosis or exfoliative dermatitis.

**Attachment 3: Transforming the on-site assessments and diaries of solicited AEs into analysis format**

When creating the analysis dataset for solicited AEs, solicited AEs (recorded by day on the SR and FA domains) need to be converted into the same format as unsolicited AEs (recorded by event). For this purpose, the start date of the AE will be considered as the date of first occurrence of the solicited AE. If on subsequent day(s), the same grade is reported, the last reported date is used as the end date of the AE. A new record is created in case the grade of the event changes. If there is a time gap of at least one day between two (or more) occurrences of the same solicited AE, then the second (and/or next) occurrence will be considered as a new AE. In case no data is reported for a day, this is analyzed as no event reported. If the on-site assessment differs in grade or relatedness with the Day 1 diary data, the on-site assessment should be recorded as a separate record in the database.

The example below shows how the solicited AE should be converted into a format of unsolicited AEs:

**Data from the Subject Diary**

Subject: 0001

Solicited systemic AE: Headache

	On site assessment	DIARY DATA							
Solicited AE	Day 1 01Jan16	Day 1 01Jan16	Day 2 02Jan16	Day 3 03Jan16	Day 4 04Jan16	Day 5 05Jan16	Day 6 06Jan16	Day 7 07Jan16	Day 8 08Jan16
Grade	2	1	1	0	3	3	1	0	0
Relatedness	Doubtful	Probable							

The data should be converted and stored in the AE dataset as follows:

Subject No.	AE	Start Date (Char)	Stop Date (Char)	Severity	Relatedness	AEID
0001	Headache	01Jan16	01Jan16	2	Doubtful	1
0001	Headache	01Jan16	02Jan16	1	Probable	1
0001	Headache	04Jan16	05Jan16	3	Probable	1
0001	Headache	06Jan16	06Jan16	1	Probable	1

If a solicited AE ends after day 8:

- The last day that AE was reported and the maximum severity (or/and diameter for local AEs) after Day 8 are captured in the CRF. For this a separate record needs to be created, in case this severity deviates from the previous record.

For the **calculation of duration**, the first and last day is used, irrespective of whether interruptions occurred in between by missing reporting days or Grade 0 events. In the above

example, the 4 records contribute to the same AE, therefore AEID (AE identification) is set to the same value and the duration of the AE is set to 6 for all records.

**Notes:**

- For solicited AEs time should not be taken into account to allocate an event to a phase, the event is per definition of solicited AEs collected post-dose and should therefore not be allocated to inactive phases.
- To complete the start and end-date based on diary data, the date will be calculated based on the day the AE is reported relative to vaccination and not on the reported date. For example, if the vaccination is on 1st JAN2016, and the AE starts on DAY 3, the start date will be set to the 3rd of January 2016 independent of the reported actual date.
